### 7.3 Study procedures

Patients will be seen in accordance with the schedule listed in the table below.

[figure not shown]

Table of all measurements and procedures performed in the study.

	Run in - 30 days	T0 Baseline	T1 Day 4-5	T2 Day 25-30	T3 Day 55-60 FMD only	T4 Day 85-90	T5 Day 170-180
In- & exclusion criteria			x				
Written informed consent			x				
Randomization			x				
Baseline characteristics			x				
SDF imaging			x			x	x
Survey			x			x	x
Urine collection a		x	x			x	x
Blood pressure		x		x	x	x	x
Blood sampling		x				x	x
Anthropometric measurements	x	x				x	x
Glucose monitoring		x	x	x	x		
Adverse events			x	x	x	x	x

aFirst morning urine of the morning of the study visit

## Study visits

Patients are instructed to not eat or smoke the morning of the study visit.

## Baseline characteristics

Baseline characteristics will be obtained at the beginning of the study which includes: date of birth, age, sex, ethnicity, relevant medical history, smoking, experience of hypoglycemia in the past and use of medication.

## Surveys

The EuroQol 5 Dimensions 5 Levels questionnaire (EQ-5D-5L) will be used to measure the health-related quality of life of the patients. The EQ-5D-5L is an internationally validated questionnaire to measure the health status. It contains 5 health dimensions; mobility, self-care, usual activities, pain/discomfort, anxiety/depression and a scale to score the patients' health that current day. [50]

Patients' satisfaction about the interventions will be reviewed with the Diabetes Treatment Satisfaction Questionnaire (DTSQ). The DTSQ is developed to assess the diabetes treatment satisfaction and consists of eight items each rated on a seven-point scales. The items include satisfaction with current treatment, treatment convenience, flexibility of treatment, understanding of diabetes, continuity of treatment, recommending treatment to others with diabetes and perceived frequency of hyper- and hypoglycemia. [51]

Patients will fill in the DTSQ static version at T0 and the DTSQ change version at T4.

## Urine collection

The first morning urine of the day will be collected on the day of the study visit. Levels of creatinine, albumin, heparanase, MCP-1 and HS-fragments will be measured in the urine samples. The presence of leukocytes or nitrite in the urine will be tested with a dipstick. In the FMD arm, urinary ketones will be measured after the first 5 days of the first cycle to assess the compliance of the patients. Analysis of the urine samples will be done in the LUMC and Radboud University Medical Center. The urine samples will be stored in the LUMC.

## Laboratory tests

Blood sampling will be done at 3 study visits by vena puncture. At T0, T4 and T5, serum levels of Hb, Ht, Hb1ac, C-peptide, IGF-1, total cholesterol, LDL cholesterol, HDL cholesterol, triglycerides, creatinine, C-reactive protein, MCP-1, ASAT and ALAT will be assed. Analysis and storage of the samples will be done in the LUMC.

In the FMD arm on day 5 of the first FMD cycle, blood ketone levels will be determined with a

capillary ketone meter.

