### **Blood pressure and anthropometric measurements**

Systolic and diastolic blood pressure will be measured at the study visits by hand or automatic monitor. Height in centimeters and body weight in kilogram will be measured in indoor clothing but without shoes. Waist circumference and hip circumference will be measured in centimeters.

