#### **7.4 Withdrawal of individual subjects**

Subjects can leave the study at any time for any reason if they wish to do so without any consequences. The investigator can decide to withdraw a subject from the study for urgent medical reasons or if continuing participation is deleterious for the subject's wellbeing. For example,  $\geq 20\%$  weight loss or an allergic reaction to the food supplement or diet ingredients will be a reason for withdrawal from further participation. All data generated up to the time of discontinuation from the study will be analysed and the reason for discontinuation will be documented.

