### 8.2 AEs, SAEs and SUSARs

#### 8.2.1 Adverse events (AEs)

Adverse events are defined as any undesirable experience occurring to a subject during the study, whether or not considered related to the fasting mimicking diet or food supplement. At every study visit the occurrence of an adverse event is evaluated. A telephone number is provided to all the subjects in the study in the informed consent form which they can contact in case of an (serious) adverse event during the study. All adverse events reported at the study visit by the subject or observed by the investigator or the research staff will be evaluated and recorded.

The occurrence of hypoglycemia is evaluated at every study visit in all intervention groups together with the glucose monitoring. Patients in the diet group that use sulfonylureas or insulin are instructed to call the investigator in case of hypoglycemia (see paragraph 5.3). In case of persistent or severe hypoglycemia, patients can contact the investigator on week days and the internal resident on duty at the Haaglanden Medical Center in the evening/night of weekdays and on weekend days. Treatment of hypoglycemia will be performed according to the investigator's or physician's decision and the guidelines of hypoglycemia.

Any (serious) adverse event recorded by the general practitioner or internal residents at the Haaglanden Medical Center will be reported to the investigator by email ([name] ) or by telephone as soon as possible. The investigator is responsible for evaluating and recording all adverse events.

The laboratory results will be evaluated by the investigator. An abnormality in a laboratory assessment will be documented and is left to the discretion of the investigator. If, in the opinion of the investigator, the laboratory results jeopardise the safety of the subject, the subject will be withdrawn from the study. The following results or references ranges will require additional investigation and follow-up:

- ASAT and ALAT level  $\geq$  than two times the baseline value.
- Creatinine level increase of more than 25% of the baseline value.
- CRP level  $\geq$  10 mg/dl.

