Patients receiving the fasting mimicking diet can return to their normal diet if there is a high incidence of adverse effect during the 5 days of the diet. Because of the low caloric intake during the diet, adequate measures are taken to prevent hypoglycemia induced by insulin or sulfonylureas. The dosages of these drugs are altered during the 5 days of the diet and patients are instructed to self-measure fasting glucose levels. At baseline, the instruction and

materials for self-measuring is provided to patients that use insulin or sulfonylurea derivatives. Moreover, a patient letter with the symptoms of hypoglycemia and instructions on what to do if the glucose level drops to 4.0 mmol/L, is provided to these patients. Patients that use long actin insulin during the diet are instructed to measure fasting glucose levels every day and track glucose levels during the second day of the diet. Patients that return to insulin or sulfonylurea derivatives are instructed to measure fasting glucose levels the 3 days after returning to their normal diet. These patients are contacted by the investigator or research staff by telephone. They are instructed to call the investigator if the glucose level drops to 4.0 mmol/L. At the end of the month, the last FMD cycle is evaluated for all patients together with additional glucose monitoring with a finger prick blood sample. If needed the dosages of hypoglycemic drugs can be altered. If the patients experience an allergic reaction to one of the ingredients of the Prolon diet, they are treated as mentioned in paragraph 5.4 and are withdrawn from the study. Effects on liver and kidney function are monitored during the study. The occurrence adverse effects is documented and evaluated at the end of every month.

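### Scheduled liver, kidney and weight values first become available at T4, after all diet days and nearly all capsules, so the safety thresholds that depend on them cannot be read earlier on scheduled data

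*Combined protocol and SAP*

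**What the plan says.** Section 7.3, Laboratory tests: "Blood sampling will be done at 3 study visits by vena puncture", and then "At T0, T4 and T5, serum levels of Hb, Ht, Hb1ac, C-peptide, IGF-1", in a list that goes on to creatinine, C-reactive protein, ASAT and ALAT. The blood row of the schedule table carries the same three marks.

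The table row "Anthropometric measurements" is marked at run-in, T0, T4 and T5. The accompanying text says only that "body weight in kilogram will be measured in indoor clothing but without shoes" and names no visit.

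Four places depend on these values:

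- Section 7.1.3 makes ASAT, ALAT and serum creatinine safety endpoints.
- Section 8.2.1 asks for further work-up and follow-up when ASAT and ALAT are at or above, in its words, "than two times the baseline value", when creatinine rises more than 25% from baseline, or when CRP reaches an absolute limit. Separately, if the investigator judges that "the laboratory results jeopardise the safety of the subject, the subject will be withdrawn from the study". Section 7.4.1 has a matching criterion, also left to the investigator's opinion.
- Section 7.4 gives a loss of at least 20% as an example: "weight loss or an allergic reaction to the food supplement or diet ingredients will be a reason for withdrawal from further participation".
- Section 12.1 j says of the diet: "Effects on liver and kidney function are monitored during the study". It says much the same of the supplement, and sections 10.3 and 12.2 repeat the statement.

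Section 7.6 ends study follow-up for withdrawn patients, apart from following adverse events. It points to a section 9.4 that does not exist; the relevant text is in 8.4.

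**The concern.** A threshold defined against baseline is useful for managing exposure only if a second value arrives while exposure can still be changed. Under this schedule the second value arrives after the diet is finished and when the capsules are almost used up. Section 12.2 acknowledges that the diet has not previously been given to patients with diabetes, and eligibility extends down to a CKD-EPI just above 45. A reader of section 12 would reasonably expect liver and kidney results to inform treatment while it is being given.

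There is also a cost to the data. The legacy analysis in section 9.2 compares baseline with 6 months within each group. If a patient is withdrawn because of a T4 result, section 7.6 removes the T5 measurements. The missing values then belong to patients with a possible harm signal, at a time when there is almost no treatment left to stop.

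**Working it through.** **Inputs.** Visit days and marks come from the table in 7.3. Section 5.1 gives three cycles of 5 diet days and 25 normal days, and 4 capsules per day for 3 months. Assumptions: both interventions start on Day 1 (T1 at Day 4-5 falls at the end of the first diet period, which fits), and 3 months is 90 days.

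**The plan's own count.** The blood row has marks at T0, T4 and T5, which is 3 visits. This agrees with the text of 7.3 and with section 10.3.

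**Exposure.** Diet cycle k (k = 0, 1, 2) runs from Day 30k + 1 to Day 30k + 5: Days 1-5, 31-35 and 61-65, or 15 days in all. Capsules due by Day d are 4 × d, out of 4 × 90 = 360.

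| | T0 | T1 (Day 4-5) | T2 (Day 25-30) | T3 (Day 55-60) | T4 (Day 85-90) | T5 (Day 170-180) |
|---|---|---|---|---|---|---|
| Blood for ASAT, ALAT, creatinine, CRP | x | – | – | – | x | x |
| Weight | x | – | – | – | x | x |
| Diet days done, of 15 | 0 | 4-5 | 5 | 10 | 15 | 15 |
| Capsules due, of 360 | 0 | 16-20 | 100-120 | 220-240 | 340-360 | 360 |

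Weight is also marked at run-in.

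**Results.**

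- Scheduled serum or weight values at T1, T2 and T3: none.
- Gap from the last diet day to T4: 85 − 65 = 20 to 90 − 65 = 25 days.
- Capsules due by T4: 340/360 = 94% to 360/360 = 100%, leaving 90 − 85 = 5 days at most.
- At T2, 10 of 15 diet days (two thirds) are still to come; at T3, 5 of 15 (one third). Visits therefore exist while exposure can still change, but they collect none of these values.

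**Firmness of the inputs.** The laboratory part rests on both text and table. The weight part rests on the table alone, and the table as extracted has displaced marks in other rows (consent and randomisation appear under T1). The urine mark at T1 does not fill the gap, because section 7.1.3 names serum creatinine for kidney monitoring.

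**T5 loss.** The documents give no expected rate of withdrawal at T4, so the loss cannot be sized. Each such patient is 1/23 = 4.3% of the completers planned per arm. T4 data already collected are kept, since section 7.4 analyses everything generated up to discontinuation.

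**The case against.** The strongest reply is that the plan does not contradict itself. The study lasts 6 months, so T4 and T5 do fall within it. Section 10.3 openly states that blood is taken at three time points and that liver and kidney effects are not expected. Section 12.1 e reports that kidney and liver parameters stayed within physiological ranges in the diet pilot, although in healthy volunteers. All of this stands: the monitoring statement is not literally false, and the schedule is disclosed.

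Several stronger readings are tempting, and the documents do not support them:

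- A reader might infer that no safeguard works during treatment. Between T0 and T4 there are adverse-event reviews, fasting glucose, blood pressure, home glucose testing with telephone contact for patients at risk in the diet arm, and a contact number for all. Section 8.4 allows extra tests when an event is followed. Withdrawal for an adverse event or urgent medical reason is possible at any time.
- A reader might treat the 8.2.1 limits as automatic withdrawal rules. They call for investigation; withdrawal on laboratory results is the investigator's judgement.
- A reader might say that no safety value in any arm is taken on treatment. A T4 sample before Day 90 is still within the capsule period, and finger-prick glucose is measured on treatment.
- A reader might say that follow-up stops entirely on withdrawal. Adverse events are still followed; what is lost is the set of T5 outcome measurements.

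The weight limit is also only an example, and a remote one. The diet supplies 3 × (1,090 + 4 × 725) = 11,970 kcal over 15 days (section 6.5.1). Assuming expenditure of 1,800-2,500 kcal per day and 7,700 kcal per kg, the diet days account for (27,000 − 11,970)/7,700 = 2.0 kg to (37,500 − 11,970)/7,700 = 3.3 kg. At an assumed body weight of 60-90 kg, a 20% loss is 12-18 kg.

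After these concessions one gap remains: a change in liver or kidney function without symptoms has no scheduled route to detection until T4.

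**Conclusion.** The point holds for scheduled data. The 8.2.1 laboratory thresholds and the 7.4 weight criterion cannot be read until T4, when 15 of 15 diet days and about 94-100% of capsules are done. Section 12 nevertheless presents liver and kidney monitoring as part of how effects are managed. The conflict is between what that argument implies and what the schedule can deliver; it is not a false statement. The T5 loss is real but of unknown size, and it arises only if the investigator withdraws the patient at T4.

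The conclusion assumes a Day 1 start, a 90-day capsule period and, for weight, that the anthropometry row was extracted correctly. Severity is moderate. The primary endpoint is unaffected, because the Microvascular Health Index at T4 is collected under the existing schedule and kept.

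**What to change.** 1. Reconcile section 7.3 (table, Laboratory tests, anthropometry) with 7.4, 7.4.1, 7.6, 8.2.1, 10.3, 12.1 j and 12.2. Either the schedule provides these values while exposure can still change, or the risk text says that scheduled liver, kidney and weight checks come only at the end of the intervention. The sponsor decides which route and which clinical rule apply.
2. Record body weight at the T2 and T3 visits that already take place, and name the visits in the anthropometry text. First settle whether T3 applies to the capsule arms: the table as extracted labels it for the diet arm only, whereas section 5.3 lists T3 for the capsule arms and sections 6.8.2 and 6.8.3 hand out capsules at the end of the second month.
3. State in 7.6 that withdrawal at or after T4 does not cancel the T5 outcome measurements if the patient agrees, and correct the reference to 8.4.

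Cost: one protocol amendment and a few minutes per visit. If the sponsor adds earlier values and a patient is withdrawn before T4 as a result, section 7.6 as it stands would also end collection of that patient's T4 primary measurement, so the amendment should say how this is handled.

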### **Renal function**

The CKD-EPI formula will be used for GFR estimation [52].

### **Blood pressure and anthropometric measurements**

Systolic and diastolic blood pressure will be measured at the study visits by hand or automatic monitor. Height in centimeters and body weight in kilogram will be measured in indoor clothing but without shoes. Waist circumference and hip circumference will be measured in centimeters.

### **Glucose monitoring**

Glucose monitoring is explained in paragraph 5.3.

### **SDF imaging**

Sidestream dark field (SDF) imaging is a non-invasive technique that measures the endothelial glycocalyx with a handheld camera that visualizes the sublingual microvasculature. The CE-marked camera is put under the tongue of the patients and measures in total about 3000 vascular segments in the sublingual vessels. The investigator moves the camera to a different location in the mouth until the total amount of frames necessary is determined automatically. This takes about 2-4 minutes.

The camera uses green LED light to detect the hemoglobin in red blood cells and measures lateral red blood cell (RBC) movements, RBC filling percentage, vessel density, and local vascular perfusion efficiency. These parameters reflect the endothelial glycocalyx health status and are affected if the glycocalyx layer is impaired [32, 33]. The image acquisition is automatically mediated through the Glycocheck software (Glycocheck BV, Maastricht, the Netherlands), which combines these parameters and calculates the Microvascular Health Index (MHI). This index ranges from 0.00 to 10.00 with a score between 0.00 – 1.00 reflecting a clinically perturbed glycocalyx and perfusion in the microvasculature, a score between 1.00 – 2.00 a less than average health of the microvasculature, 2.00 – 3.00 an average microvascular health, between 3.00 and 5.00 an above average and a score above 5.00 a good functional microcirculation with adequate endothelial glycocalyx coverage and flow mediated adaptation.

In addition, capillary tortuosity will be determined by placing the SDF camera in four quadrants of the inner lip (duration about 1-2 minutes): the upper right quadrant, upper left quadrant, lower right quadrant and lower left quadrant. From these collected frames, the

capillary tortuosity will be assessed by scoring the number of twists per capillary in the capillaries in the field of view per image. The number of twists will be stratified as 0: no twists (or pinhead capillaries) to 4: four or more twists, described by Djaberi et al. [53] The overall tortuosity score per subject will be determined by selecting the most frequent tortuosity score in the 12 studied microcirculatory imaging areas (3 microcirculatory imaging areas per quadrant).

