### 3. STUDY DESIGN

A 6-month, single center randomized controlled trial to study the effects of dietary interventions on improving endothelial health in South Asian patients with diabetic nephropathy. In total 90 South Asian patients with type 2 diabetes and proven microalbuminuria between 18-75 years of age will be recruited at general practitioner centers in the The Hague region. Eligible patients will be included for a period of 6 months. Patients will be randomly assigned to receive the fasting mimicking diet, food supplement or placebo for a period of 3 months. The primary endpoint is an improvement of the Microvascular Health index after 3 months in the diet group compared to the placebo group and in the food supplement group compared to the placebo group, measured with SDF-imaging. After 6 months, which is 3 months after stopping with the interventions, patients will also return for a follow-up measurement to investigate possible legacy effects of each intervention.

The food supplement and placebo arm will be double blinded. The placebo arm will also be used as a control group for the FMD arm.

Study procedures will take place at the practice of the general practitioner and will be performed by LUMC research staff. The general practitioner will not perform any of the study procedures. Flow chart I gives an overview of the study design and time points for study visits.

Flow chart I

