### FMD group

Patients that use sulfonylureas or insulin will be provided with a glucose meter and strips at baseline. The device and strips will be provided for free. These patients will get an instruction from the investigator or research staff on how to self-measure glucose levels.

Patients are asked at baseline if they have ever experienced hypoglycemia. The symptoms of hypoglycemia are explained and provided in a patient letter to patients that use sulfonylureas or insulin. The patient letter contains a telephone number and instructions on what to do if the patient experiences symptoms of hypoglycemia or if the self-measured glucose drops below 4.0 mmol/L. Patients are instructed to call the investigator if they experienced hypoglycemia during weekdays and the internal resident on duty at the Haaglanden Medical Center in the evening/night of weekdays and on weekend days.

Treatment of hypoglycemia will be performed according to the investigator's or physician's decision and the guidelines of hypoglycemia. The dosages of the hypoglycemic medication can be adjusted if needed.

[figure not shown]
To prevent hypoglycemia during the diet, the dosages of oral hypoglycemic drugs and insulin will be altered during the 5 days of the diet. These alterations are shown in flow chart II.

Sulfonylurea's and rapid acting insulin will be stopped, and the dosage of long acting insulin will be halved during the 5 days of the diet. The sulfonylurea drugs will be stopped one day prior to the start of the diet. Metformin will be continued during the diet. Patients that still use long actin insulin during the diet are asked to measure fasting glucose levels during the 5 days and track glucose levels 4 times throughout the second day of the diet. These patients will be contacted by the investigator during the diet to monitor the glucose levels.

Patients will return to their normal dosage of oral hypoglycemic drugs or insulin for the next 25 days of the month. Patients that return to sulfonylureas or long- or rapid acting insulin are instructed to measure the fasting glucose for the first 3 days after the diet. The investigator or one of the research staff will contact these patients by phone in the first following days after returning to their normal diet.

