At the end of every month, the previous FMD cycle is evaluated together with the glucose monitoring, by measuring fasting glucose levels with a finger prick blood sample. Patients that use rapid acting insulin are instructed to track glucose levels during one day (before every meal and before going to bed in the evening) in the week prior to the study visit. If the fasting glucose at the study visit is between 4.0 and 15.0 mmol/L and the patient did not experience hypoglycemia during that month, the dosage (for that patient) of hypoglycemic drugs is not altered. However, if the patient did experience hypoglycemia during that month or the measured fasting glucose at the study visit is below 4.0 mmol/L, the dosage of hypoglycemic drugs will be altered according to the investigators opinion.

Flow chart II: Hypoglycaemic drug dosage adjustment during the 5-day FMD

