## **6.8 Drug accountability**

### **6.8.1 Fasting mimicking diet**

The Prolon boxes will be stored in the LUMC. The principal investigator is responsible for providing the Prolon box to the patients before the start of every cycle and is responsible for checking the expiration date on the packages in the boxes.

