### 7.2 Randomisation, blinding and treatment allocation

Eligible patients will be randomized during the run in period into the FMD, food supplement or placebo arm after given informed consent. Randomisation will be performed by the LUMC pharmacy. The placebo and food supplement group will be double blinded. The pharmacy will store the randomization code. The investigator or pharmacy can deblind the subjects in the occurrence of any AE, SAE, or abnormality in a laboratory assessment which, in the opinion of the investigator, warrants the subject's permanent withdrawal from the trial.

Patient specific data will be stored under a subject identification code and randomization number for each patient. There will be a subject identification code list that links the codes to a subject. This list will be stored for 15 years by the principal investigator. Data will be presented for the complete intention-to-treat population as well as the per protocol population.

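### The diet-placebo primary comparison is open, and the plan describes no masking of the person who takes the sublingual images behind the MHI

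*Combined protocol and SAP*

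**What the plan says.** Blinding is described for two of the three arms. Section 7.2 states: "The placebo and food supplement group will be double blinded". Section 3 then adds: "The placebo arm will also be used as a control group for the FMD arm". Sections 2, 7.1.1 and 9.1 all treat FMD against placebo as a primary comparison, alongside supplement against placebo.

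On who measures, section 3 says: "Study procedures will take place at the practice of the general practitioner and will be performed by LUMC research staff". The SDF imaging text in section 7.3 is more specific about the sublingual images: "The investigator moves the camera to a different location in the mouth until the total amount of frames necessary is determined automatically". It fixes four lip quadrants for the separate tortuosity images but names no sites or sequence under the tongue.

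On who handles the intervention, section 6.8.1 says: "The principal investigator is responsible for providing the Prolon box to the patients before the start of every cycle". Sections 6.8.2 and 6.8.3 give the handing out of capsules to the investigator. Section 5.3, on FMD patients who stay on long-acting insulin during the diet, says: "These patients will be contacted by the investigator during the diet to monitor the glucose levels". The same section also says: "At the end of every month, the previous FMD cycle is evaluated together with the glucose monitoring". It does not say by whom.

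Three other statements bear on the point. Section 7.3 says that the software mediates image acquisition and computes the MHI. Section 11.1 enters patients in that software under a subject code, with only sex added. Section 7.2 places randomisation in the run-in period, before the baseline image.

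**The concern.** Patients cannot be masked to a five-day diet, so masking the person who measures the outcome is the main protection available for the FMD comparison. The plan does not provide it. The role that hands out boxes to one arm and capsules to the others is the role named as moving the camera, and at month 3 the review of the last diet cycle falls at the visit where the primary image is taken. Nothing in the plan keeps the arm from being known or discussed before imaging.

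The operator decides where the camera goes under the tongue. If that choice, or the care taken over acquisition, differs by arm, the MHI difference between FMD and placebo picks up a component that is not an effect of the diet, and the analysis in section 9.1 cannot separate the two. Supplement against placebo is not exposed in this way, because both arms take blinded capsules.

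**Working it through.** **Is a masked operator described anywhere?**

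| Question | Where | What is found |
|---|---|---|
| Which arms are blinded? | 3, 5.1, 7.2 | Supplement and placebo only |
| Who performs procedures? | 3 | Research staff of the centre; no separate masked assessor |
| Who moves the camera? | 7.3 | The investigator; sublingual sites not fixed |
| Who hands out boxes and capsules? | 6.8.1 to 6.8.3 | The principal investigator (boxes), the investigator (capsules) |
| Who contacts FMD patients? | 5.3 | The investigator, for long-acting insulin users during the diet; the investigator or research staff, for those returning to sulfonylureas or insulin afterwards |
| Who stops acquisition and computes the MHI? | 7.3 | Software |
| How are files labelled? | 11.1 | Subject code and sex |

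No section masks the operator or separates diet handling from imaging. The software and the coded files act around or after the choice of site. A code in a file does not mask the person holding the camera in front of the patient.

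**The plan's own sample size.** Inputs from section 4.4: difference 0.35, SD 0.41, two-sided alpha 0.05, 23 per group, 80% power.

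- Standard error of the difference = 0.41 × √(2/23) = 0.121.
- Noncentrality = 0.35 / 0.121 = 2.89 on 2 × 23 − 2 = 44 degrees of freedom; critical value 2.015.
- Power from the noncentral t distribution = 80.8% (79.0% at 22 per group). The stated 23 is reproduced.

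**Sensitivity to a measurement shift.** The documents give no operator error and no bias size. The shifts b below are assumptions. Set the true effect to zero, add b to the FMD-placebo difference, and compute the chance that the same test is significant in favour of FMD: P(T > critical value), with T noncentral t and noncentrality b / SE.

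| Assumed shift b (MHI units) | b / 0.35 | b / SE, 23 per arm | Significant for FMD, 23 per arm | Significant for FMD, 30 per arm |
|---|---|---|---|---|
| 0 | 0% | 0 | 2.5% | 2.5% |
| 0.05 | 14% | 0.41 | 6.0% | 6.7% |
| 0.10 | 29% | 0.83 | 12.5% | 15.1% |
| 0.15 | 43% | 1.24 | 22.8% | 28.6% |

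For 30 per arm, SE = 0.41 × √(2/30) = 0.106. The rates count only results favouring the diet, since that is the error at stake; their unbiased reference is 2.5%, not 5%. A larger sample makes the problem worse, because a fixed shift is then judged against a smaller standard error.

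**Which visits?** The endpoint is a change from baseline. Because randomisation precedes the baseline image, T0 is exposed as well as T4 and T5. Protecting baseline alone would leave the outcome visits open.

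**The case against.** The best defence is that little is left for the operator to influence. The software mediates acquisition, samples about 3000 vascular segments, decides when enough frames exist and calculates the index. Nothing says that the operator sees the MHI, or any glycocalyx reading, while moving the camera, so a shift in a particular direction is conjecture. This stands as a limit on the likely size. It does not close the gap, because the sites are still chosen by someone who may know the arm.

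Four stronger readings are tempting, and the documents do not support them.

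- **The operator knows the arm.** This is a reasonable inference from the tasks given to the investigator role, but it is not stated. Section 3 speaks of research staff, section 6.8.1 of the principal investigator and section 7.3 of the investigator; these may be different people.
- **The investigator follows every FMD patient through each cycle.** The planned calls cover only some users of insulin or sulfonylureas, calls after the diet may be made by research staff, and the month-end review names nobody. An eligible patient on metformin alone has no planned call.
- **Subjective reading of images affects the primary result.** Section 7.3 does say that "capillary tortuosity will be assessed by scoring the number of twists per capillary", with no masking of the reader stated. But tortuosity is not listed in section 7.1 and is not described as part of the MHI. That the scoring is done by eye is itself an inference, and the subject code might mask an offline reader, though the plan does not say so.
- **The table shows how far the trial will be biased.** Any unmasked measurement would yield such a table. It shows sensitivity, not evidence that a shift exists.

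It is also fair to object that team size at the practice visits is not given, so separating the roles may not always be possible.

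**Conclusion.** The gap is real and should be closed. FMD against placebo is an open primary comparison, and no masking of the SDF operator is described for it at any imaging visit. The remaining route to bias in the MHI is site choice and image acquisition; its size and direction are unknown. If a systematic shift of 0.05 to 0.15 MHI units favouring the diet arose, false significance in its favour would rise from 2.5% to between 6.0% and 22.8% at 23 per arm. That range rests on the plan's SD of 0.41 and on shifts that are assumed.

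The documents do not support saying that the operator is in fact unmasked, or that the FMD result will be inflated. They support saying that, as written, a positive FMD finding could not be separated from operator expectation. The supplement comparison and the sample size are unaffected.

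**What to change.** In section 7.3, state that at T0, T4 and T5:

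- SDF imaging is the first procedure of the visit;
- it is done by a member of the existing research staff who has had no diet supply or diet contact with that patient and is not told the arm;
- the patient is asked beforehand not to disclose the arm.

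Where the roster cannot separate the roles, record whether the operator knew the arm, and state in the report that the FMD comparison was not assessor-masked for those patients.

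As a side point for the unlisted tortuosity measure, recode the lip images so that the reader sees neither arm nor visit, and score them in random order.

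The cost is some rostering, a fixed order within the visit and a file-renaming step. No visit, procedure, post or patient is added. Some patients will reveal their arm, so masking will occasionally fail.
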